## **7 STUDY POPULATION**

### **7.1 Number of Subjects**

Study population includes 525 eligible early stage untreated PD patients who are not early terminated from the study during screening or baseline visits. Subject will be recruited from approximately 70 sites in North America and Europe.

### **7.2 Subjects Enrolment**

All subjects enrolled must be eligible as per Inclusion/Exclusion Criteria. Personal interview including medical history, physical and neurological examination, and evaluation for trial eligibility will be done as specified in Schedule of Activities, Appendix I.

### **7.3 Inclusion Criteria**

Subjects must meet all the inclusion criteria to be eligible:

1. Subject is informed and given ample time and opportunity to think about his/her participation in this study and has given his/her written informed consent on an EC/IRB approved consent form.
2. Subject is willing and able to comply with all study requirements (protocol, clinic visits, procedures and medication administration).
3. Subject is male or female  $\geq 35.0$  years of age to  $\leq 80.0$  years of age at the time of enrollment
4. Subject has Parkinson's disease consistent with the UK Brain Bank Criteria and must have bradykinesia with sequence effect. If rest tremor does not exist must have prominent asymmetry of motor function.
5. Subject with disease duration less than 3 years since diagnosis.
6. Subject has a H&Y stage score of  $< 3$ .

7. Subject has a MMSE score  $\geq 26$ .
  8. Women of child-bearing potential (WOCBP)\* must use a reliable method of contraception (e.g., oral contraceptive or long-term injectable or implantable hormonal contraceptive, double-barrier methods [such as condom plus diaphragm, condom plus spermicide foam, condom plus sponge], or intra-uterine devices) for the entire study duration, and must have a negative serum pregnancy test at Screening and negative urine pregnancy at baseline visit.
  9. Subject was approved by a central Eligibility Monitoring Committee (EMC) based on suitability for the study, and his/her eligibility was confirmed by EMC signature on the Randomization Authorization Form (RAF).
- \*WOCBP are defined as any female who has experienced menarche and who is NOT permanently sterile or postmenopausal. Postmenopausal is defined as 12 consecutive months with no menses without an alternative medical cause.

#### **7.4 Exclusion Criteria**

Subjects are not permitted to enroll in the study if any 1 of the following criteria is met.

1. Subject has previously participated in this study.
2. Subject has participated in another study of an investigational medicinal product (IMP) or a medical device within the last 30 days or is currently participating in another study of an IMP or medical device.
3. Subject has an atypical parkinsonian syndrome or secondary parkinsonism (e.g., due to drugs, toxins, metabolic disorders, encephalitis, cerebrovascular disease or degenerative disease).
4. Subject has a history of psychosis or hallucinations within the previous 12 months.
5. Subject has cognitive impairment in the judgment of the Investigator that excludes him/her from understanding consent or participating in the study.
6. Subject has previous exposure to levodopa or a dopamine agonist for longer than 4 weeks; if previous exposure was less than 4 weeks then it must not be within 2 months prior to the baseline visit.

7. Subject has previous exposure to a MAO-B inhibitor for longer than 4 weeks; if previous exposure was less than 4 weeks then it must not be within 3 months prior to the baseline visit.
8. Subject who has taken anticholinergic drugs for PD or amantadine for longer than 4 weeks; if previous exposure was less than 4 weeks then it must not be within 1 month prior to the baseline visit.
9. Subject who is taking non-selective MAO inhibitors.
10. Subject who is taking potent CYP1A2 inhibitors, e.g, Ciprofloxacin
11. Subject who is taking antitussive agent dextromethorphan.
12. Subject who is taking analgesic agents such as tramadol, meperidine, methadone and propoxyphene.
13. Subject who is taking strong 3A4 inducers, e.g., St. John's Wort or cyclobenzaprine (tricyclic muscle relaxant).
14. Subject who is taking dopamine antagonists, such as the neuroleptics (phenothiazines, butyrophenones, thioxanthenes) or metoclopramide.
15. Marijuana or previous exposure to Marijuana during the last 30 days prior to the baseline visit or subject has a history of alcohol or drug abuse or dependence within the prior 12 months, according to Investigator judgment, (alcohol intake is limited to 1 glass or shot per day during the whole study taken not less than 3 hours before or after dosing (see section 10.2).
16. Any relevant medical, surgical, or psychiatric condition, laboratory value, or concomitant medication which, in the opinion of the Investigator, makes the subject unsuitable for study entry or potentially unable to complete all aspects of the study.
17. Subject has severe or moderate renal impairment (creatinine clearance <50 mL/min) or on dialysis.
18. Subject has moderate (Child-Pugh categorization B, score 7-9) or severe (Child-Pugh categorization C, score 10-15) hepatic impairment ( Lucey MR, 1997).

19. Subject has a lifetime history of suicide attempt (including an active attempt, interrupted attempt or aborted attempt), or has suicidal ideation in the past 6 months as indicated by a positive response ('Yes') to either Question 4 or Question 5 of the Columbia-Suicide Severity Rating Scale (CSSRS) at Screening.
20. Subject has known hypersensitivity or intolerance to pramipexole or rasagiline or to any components or excipients of the test drug or placebo.
21. Subject who has a history of neuroleptic malignant syndrome.
22. Subject who is pregnant or breastfeeding.
23. Subject, who, for any reason, is judged by the Investigator or the EMC to be inappropriate for this study, including a subject who is unable to communicate or cooperate with the Investigator or who has/had a clinically significant illness or abnormal physical examination that may compromise safety of the subject during the trial or affect ability of the subject to adhere to study procedures.

A site will not be allowed to randomize subjects unless their diagnosis and suitability for the study has been confirmed and documented by both the Investigator and the EMC and they are deemed to be a satisfactory candidate by the EMC.

### **7.5 Early Discontinuation Subjects**

A subject can leave the study at any time for any reason without consequences, upon request. The protocol distinguishes between two types of early Terminations:

- Early Treatment Termination (ETT)
- Early Study Termination (EST)

#### Early Treatment Termination (ETT)

A subject who discontinued study medication for any reason before the end of week 12 will continue pre-planned study schedule of activities as follow up. The subject will be requested to undergo a treatment termination visit as described in section 9.2.11

Please note that P2B001/PPX 0.6/RAS 0.75/Placebo capsules can be stopped immediately, while pramipexole ER/matching placebo tablets need to be gradually down titrated as described in section 6.1.

The reasons for withdrawal could include the following:

- Subject withdrawal of consent to be treated with study medication(s) but still consenting to participate in study visits and activities
- Request of the Investigator for any medical or other reason
- Request of the primary care physician via the Investigator
- Pregnancy
- Non-compliance
- Subject who cannot achieve the minimum therapeutic dose of pramipexole ER (or placebo) of 1.5 mg per day.
- Major protocol violation
- Adverse Event/Experience
- Lack of Efficacy
- Subjects who, according to the Investigator, need additional therapy that is excluded in the protocol for the treatment of the disease.
- Any other reason relating to the patient's safety or integrity of the study data.

If a subject suspect that she is pregnant, a urine test will be performed at the site. If the urine test is positive, study drug administration will be interrupted pending the results of a confirmatory blood/serum test. If the pregnancy is confirmed with a positive blood/serum test, then the subject will be permanently discontinued from study drug, but should participate in a Treatment Termination visit and continue with all the study visits as follow up visits up to and including safety follow up visit at week 14. The PI will follow the subject until she has given birth.

On completion of the dose-titration phase (end of week 6), the minimum therapeutic dose of pramipexole ER 1.5 mg per day (or placebo) must be achieved by all the patients. The treatment with study medications of patients who cannot achieve this dosage will be discontinued, but the subject will be requested to continue with all the study visits.

#### Early Study Termination (EST)

A subject who requests to stop study participation for any reason before the end of week 12, including study treatment and study scheduled activities, will be requested to undergo a study termination visit as described in section 9.2.11, unless erroneously randomized or withdrew consent prior to first dose.

The reasons for EST could include the following:

- Pregnancy
- Adverse Event/Experience

- Subject withdrawal of consent and refusal to continue participation in study due to lack of efficacy or due to other reasons
- Lost to follow-up/failure to return
- Death
- Erroneously randomized
- Withdrew consent prior to first dose

If there is a medical reason for withdrawal and the subject refuses to come to study visits after study medication was stopped, the subject will remain under the supervision of the PI as long as the PI deems medically necessary.

## **7.6 Subject Replacement**

A subject who leaves the study at any time for any reason will not be replaced.

# **8 ASSESSMENTS**

## **8.1 Schedule of Activities**

See Appendix I for a table describing activities performed at each visit.

## **8.2 Evaluation of Pramipexole ER (or Placebo) Dose**

The subject will be required to visit the clinic at the end of week 3 and 5 (visit 3 and 4) and be available for a phone call at the end of week 4 for titration evaluation; to assess the tolerability and efficacy of the pramipexole ER (or placebo) and the possible need for changing the pramipexole ER dose.

## **8.3 Safety and Tolerability**

### **8.3.1 Physical and Neurological Exams**

A complete physical exam (consisting of a review of all body systems) and neurological exam (including evaluation of mental status; motor function; balance and coordination; sensory function; reflexes and cranial nerves) at visit 1 will be conducted by the study neurologist (primary Investigator or sub-Investigator). On visit 7 and unscheduled visits a symptom-directed physical and neurological exam will be performed by the study neurologist.

### **8.3.2 Safety Laboratory Tests – see Appendix II**

Hematology, chemistry and urinalysis tests will be performed as general measures of health. Eurofins Scientific will be responsible for shipment, storage, and testing of all laboratory samples. Instructions will be included in the laboratory manual.

### **8.3.3 ECG**

12-lead ECGs will be performed to evaluate the cardiovascular system on the screening and baseline visits and on visit 7.

### **8.3.4 Vital Signs**

Vitals signs will be measured at all visits except for Visit 3. Blood pressure and pulse will be recorded after resting supine for 5 minutes and standing after at least 3 minutes. Orthostatic hypotension is defined as a reduction of systolic blood pressure of at least 20 mm Hg or 10 mm Hg in diastolic blood pressure within 3 minutes of quiet standing (Aronow WS, 2011). Height will be measured at screening only and weight will be measured at all visits.

#### ***8.3.4.1 Orthostatic Hypotension Evaluation***

1. On baseline and visits 4, 5 and 6, subjects that have OH according to the description above (section 8.3.4) will be asked to answer one question of the orthostatic hypotension activity scale (OHAS) which inquires about dizziness, lightheadedness, feeling faint or feeling as though you might pass out. The answer is a scale from 0 to 10 where 0 is none and 10 is the worst possible.
2. Change in the differences in systolic and diastolic blood pressure measured during supine and standing positions.

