**Study activities:**

Subjects will undergo visit specific study activities at screening, baseline, end of weeks 3, 4, 5, 8, 12/Treatment Termination and a safety follow up at end of week 14 (see Appendix 1, schedule of activities).

UPDRS II +III and ESS assessments will be conducted at the baseline visit, as well as end of weeks 5, 8, and 12/Treatment Termination. UPDRS III will also be conducted at screening.

QUIP-RS will be conducted at the baseline visit, as well as end of weeks 3, 5, 8, 12/Treatment Termination and week 14. CSSRS will be conducted at every study visit.

PDQ39, CGI-S and HRQOL SF-12 v 2 scales will be conducted at baseline and end of week 12/Treatment Termination.

CGI-I will be performed at end of weeks 5, 8 and 12/Treatment Termination visits. OSHA question 1 will be completed at baseline and end of weeks 5, 8 and 12/Treatment Termination, only for subjects experiencing orthostatic hypotension.

Subjects will take study medications (capsule and tablets) by mouth with a glass of water (8oz or 240ml). Study medications can be taken with or without food and efforts should be made to take the study medications at the same time every day.

To preserve the blind the capsules of once daily P2B001/RAS 0.75/PPX0.6/Placebo will be visually identical. The tablets of the pramipexole ER and their placebos will be visually identical.

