### **9.2.3 Visit 2 - Baseline**

The time between visit 1 (screening), and visit 2 (baseline), will be no less than 24 hours and no more than 28 days (or up to 90 days with sponsor approval). In this visit a medication kit will be dispensed to him/her together with a leaflet of instructions for use. The subject will be given an emergency contact card with 24-hour contact numbers. The subject will be instructed to keep the contact card with him/her at all times.

The following activities will be performed:

- Dispensation of study medication kit
- Vital signs (HR, BP RR and temperature), weight and ECG
- Urine pregnancy test for women of childbearing potential
- Concomitant medications
- Adverse events review
- Inclusion/Exclusion criteria review
- Study drug dispensing and dosing instructions

- UPDRS II and III questionnaire
- CSSRS- SLV questionnaire
- CGI-S questionnaire
- PDQ39 questionnaire
- ESS questionnaire
- QUIP-RS questionnaire
- HRQOL SF-12v2
- Orthostatic hypotension scale question 1 for subjects with OH

The treatment should be started according to the dosing instructions the day after the baseline visit.

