**15.6.11 The exploratory endpoints to be analyzed are:**

- To evaluate the efficacy of P2B001 0.6/0.75 mg compared to its individual components in the following endpoints:
  - Change from baseline to Week 12/Treatment Termination visit in each of the 8 PDQ39 subscales scores.
  - Change from baseline to Week 12/Treatment Termination visit in Health-Related Quality of Life (HRQOL) SF-12v2 questionnaire.

- Clinical Global Impression of Improvement (CGI-I) at Week 12/Treatment Termination visit.
- To evaluate the superiority of P2B001 0.6/0.75 mg over Pramipexole ER with respect to the following outcome measures:
  - Proportion (%) of patients with ESS score >10 at Week 12/Treatment Termination.
  - Proportion (%) of patients with ESS Score  $\leq$ 10 at baseline and ESS score >10 at Week 12/Treatment Termination.
  - 3-Months rate of total number of adverse events.
  - Change from baseline to Week 12/Treatment Termination in the differences in systolic and diastolic blood pressure measured during supine and standing positions.
  - Proportion (%) of patients with both symptomatic/non-symptomatic Orthostatic Hypotension.
  - 3-Months rate of total number of both symptomatic/non-symptomatic Orthostatic Hypotension.
  - Proportion (%) of patients with symptomatic Orthostatic Hypotension.
  - 3-Months rate of total number of symptomatic Orthostatic Hypotension.
  - Proportion (%) of patients with daytime sleepiness/drowsiness related AE's.
  - Proportion (%) of patients with gastrointestinal (GI) adverse events
  - Proportion (%) of patients presenting neurological adverse events
  - Change from baseline to Week 12/Treatment Termination visit in the Orthostatic Hypotension Symptoms Assessment (OHSA) question 1.
- To descriptively evaluate the comparability of P2B001 0.6/0.75 mg with reference to the calibration arm (Pramipexole ER) in total UPDRS score (defined as sum of parts II and III, scores (0-160)).

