\*\* The maximal interval between the screening and baseline visits can be extended to 35 days, however, additional Sponsor approval will be required. 35 – 90 days may be approved but a new collection of screening laboratory samples will be required to verify eligibility prior to baseline.

\*\*\* Coagulation will also be performed at screening to determine eligibility and at visits 4 and 5 for subjects with mild hepatic impairment.

\*\*\*\* An unscheduled on-site visit may be conducted per PI's or sub-Investigator's decision to evaluate the new dose and consider the need for further dose increase.

\*\*\*\*\*height will be measured only at screening

\*\*\*\*\* OHS question 1 will be completed only by subjects experiencing orthostatic hypotension

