## 22.5 Appendix V: OHAS question 1 (Kaufmann H, 2012)

Question 1: “Dizziness, lightheadedness, feeling faint or feeling as though you might pass out”

Please circle the number on the scale (where 0 = None and 10 = Worst Possible) that best rates how severe your symptoms from low blood pressure have been on average **over the past week**. If you have not experienced the symptom, circle zero (0). PLEASE RATE THE SYMPTOMS THAT ARE DUE ONLY TO YOUR LOW BLOOD PRESSURE PROBLEM.

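### The planned change from baseline in OHSA question 1 versus pramipexole ER exists only for subjects with orthostatic hypotension at both visits, a subset selected after randomization

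*Protocol*

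**What the plan says.** Section 8.3.4 defines OH by a measured supine-to-standing drop in the first 3 minutes on the feet: "a reduction of systolic blood pressure of at least 20 mm Hg or 10 mm Hg in diastolic blood pressure". Section 8.3.4.1 then sets who answers the symptom item: "subjects that have OH according to the description above (section 8.3.4) will be asked to answer one question". The visit lists in 9.2.3, 9.2.6, 9.2.7 and 9.2.8 repeat the limit ("Orthostatic hypotension scale question 1 for subjects with OH"). So do the footnote to Appendix I ("question 1 will be completed only by subjects experiencing orthostatic hypotension") and the synopsis under Study activities ("only for subjects experiencing orthostatic hypotension"). The protocol calls the scale both OHAS and OHSA; I take these to be the same item, the one printed in Appendix V.

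Section 15.6.11 opens its list of comparisons with the calibration arm thus: "To evaluate the superiority of P2B001 0.6/0.75 mg over Pramipexole ER with respect to the following outcome measures". The last entry in that list is "Change from baseline to Week 12/Treatment Termination visit in the Orthostatic Hypotension Symptoms Assessment (OHSA) question 1". Section 15.11 lists the same endpoint again. The end of section 15.6.10.5 has exploratory endpoints tested on the ITT set at a nominal 5% without multiplicity control, and leaves the detailed methods to the SAP. The opening of section 15 and the synopsis under Statistical Methodology say something different: apart from the ESS, comparisons with pramipexole ER are descriptive, with no formal testing.

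**The concern.** The collection rule and the endpoint do not fit together. A change score needs two answers, and an answer is collected only when OH is present. A subject who develops OH on study drug has no baseline score. A subject whose OH resolves has no final score. Both drop out of the comparison.

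The baseline half of the condition does no harm to randomization, since dosing starts the day after the baseline visit (9.2.3). The second half does. OH at Week 12/Treatment Termination is a possible treatment effect and is itself compared between these two arms in 15.6.11. The subjects left in each arm may therefore differ in kind as well as in number, at any prevalence of OH.

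At stake is one exploratory endpoint. The risk is that a nominal p-value from a small, non-randomized subset is reported as a comparison of symptom severity with pramipexole ER.

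**Working it through.** **Plan's own figure.** No sample size, power or expected OH count is given for this item. The only power figure for this pair of arms is for the ESS (section 15.1): SD 3.0, difference 1.5, 150 versus 75 subjects, two-sided 5%. The standard error is 3.0 × √(1/150 + 1/75) = 0.424, and 1.5 / 0.424 = 3.54. The noncentral t with 223 df gives 94.1%, as stated. That power assumes that every subject contributes, which is not so for question 1.

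**Inputs for question 1.**
- Arm sizes 150 (P2B001) and 75 (pramipexole ER), from section 15.
- OH in the Phase 2b table (section 3.4): 4/50 (8%), 1/50 (2%) and 2/49 (4.1%). These are adverse-event reports, not prevalence at a visit.
- Prevalence at a visit by the 8.3.4 definition is not in the documents. I assume the same value in both arms and show a range.
- Persistence (OH at the final visit given OH at baseline) is not in the documents. I use independence, 50% and 100%.

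**Formula.** Expected subjects with a change score = arm size × prevalence × persistence. Under independence, persistence equals prevalence. For 8%: 150 × 0.08 × 0.08 = 0.96 and 75 × 0.08 × 0.08 = 0.48; with full persistence, 150 × 0.08 = 12 and 75 × 0.08 = 6.

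| Assumed prevalence | Independent | 50% persistence | 100% persistence |
|---|---|---|---|
| 4.1% | 0.3 vs 0.1 | 3.1 vs 1.5 | 6.2 vs 3.1 |
| 8% | 1.0 vs 0.5 | 6 vs 3 | 12 vs 6 |
| 15% | 3.4 vs 1.7 | 11.2 vs 5.6 | 22.5 vs 11.2 |
| 20% | 6 vs 3 | 15 vs 7.5 | 30 vs 15 |

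Entries are P2B001 versus pramipexole ER, before any dropout. The pramipexole ER arm exceeds 8 subjects only if prevalence × persistence is above 8/75 = 10.7%.

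**What such counts can show.** In a two-sample t-test at two-sided 5%, power for a 1 SD difference is 23% at 6 versus 3 and 47% at 12 versus 6. The difference detectable with 80% power is 2.3 SD and 1.5 SD respectively. At 12 versus 6 the 95% confidence interval half-width is 2.12 × √(1/12 + 1/6) = 1.06 SD. The SD here is that of the change among subjects with OH at both visits.

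**The case against.** **Stakes.** This is one of twelve exploratory comparisons with pramipexole ER in 15.6.11, and it has no bearing on the primary or key secondary endpoints. That stands.

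**Coverage elsewhere.** A reader might infer that the trial cannot compare OH between these arms, or misses new cases. The documents do not support that. Section 15.6.11 also lists the proportion of patients with any OH and with symptomatic OH, the 3-month rate of each, and the change in supine-standing blood pressure differences. Incidence is covered; only the severity comparison is lost.

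**Number affected.** A reader might take the small counts as established. They are not. In this protocol OH must be recorded as an adverse event only if judged clinically significant or if the drop exceeds 30 mm Hg systolic or 20 mm Hg diastolic (13.3), a higher bar than the 20/10 mm Hg definition. Prevalence at a visit could therefore exceed 8%. Also, the synopsis and Appendix I speak of subjects experiencing OH, which is looser than 8.3.4.1. The selection problem does not depend on the count.

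**Gain from asking everyone.** With all 225 subjects the half-width would be 0.28 SD, and a reader might set this against 1.06 SD and infer a nearly fourfold gain. The two SDs belong to different populations. Among all subjects most scores would be zero and the mean difference would be diluted, so that gain is not shown.

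**Reason for the restriction.** Appendix V tells subjects to rate only symptoms due to their low blood pressure problem, so limiting the item to OH has a rationale. But Appendix V also provides a zero for those without the symptom, and it asks about the past week, whereas the filter is a reading on the day. A subject with symptoms that week but no qualifying drop at the visit is not asked.

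**The SAP.** Only the addendum to SAP version 2.0 is available. The SAP takes precedence (15.13) and may hold a rule for subjects not asked, or may drop the endpoint. No rule can recover answers that were never collected, and scoring them zero would be an assumption because of the mismatch just described.

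**Conclusion.** The point holds for this exploratory endpoint. As the protocol is written, the change score can be formed only for subjects with OH at both baseline and Week 12/Treatment Termination. That conclusion rests on reading 8.3.4.1 as applying visit by visit, which is its natural meaning, and on no prevalence figure.

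The size is a range resting on assumed prevalence and persistence. With 8%, the highest Phase 2b adverse-event rate, it runs from about 1 versus 0.5 to 12 versus 6 subjects. With an assumed 20% it reaches 30 versus 15 at most. A valid between-arm comparison of OH symptom severity is lost. The conflict between the descriptive-only rule for pramipexole ER and the superiority testing in 15.6.10.5 and 15.6.11 is a separate inconsistency that also needs resolving.

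**What to change.** If collection can still change, ask question 1 of all subjects at visits 2, 4, 5 and 6 and analyse the change in all of them, up to 150 versus 75. Orthostatic blood pressure is already taken at these visits, so the cost is one 0 to 10 item and wording changes in 8.3.4.1, the visit lists, the synopsis and Appendix I. The downsides are many zeros, and that subjects without a measured drop must judge whether their symptoms come from low blood pressure.

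The addendum of November 2021 refers to a blinded data review before unblinding, so collection appears complete or nearly so. In that case, remove the change-from-baseline superiority comparison for this item from 15.6.11 and 15.11 and from the matching objectives in the synopsis and 4.3. Describe instead, by arm and visit, the proportion with OH among all subjects and the question 1 scores among those asked, stating that the latter group is selected. This needs no new data, only a SAP and protocol text change before unblinding.

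Either way, reconcile the opening of section 15 and the synopsis with 15.6.10.5 and 15.6.11 on whether comparisons with pramipexole ER other than the ESS are tested or only described. The descriptive option already fits the former.
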